8. Master Forms Set: The **S0535** Adverse Event Summary Form has been updated to allow idarubicin as an option to be used during Consolidation Cycles 3 and 4. The form number and Version Date remain the same.
9. Pages 96, 98 and 99, Appendix 19.4: The CTSU website url has been updated to www.ctsu.org throughout this section.

Additionally, please note that this study has met the criteria to proceed to the second stage of accrual. The study will not be closed pending data analysis, but will continue to complete accrual.

This memorandum serves to notify the NCI and Southwest Oncology Group Statistical Center.

cc: PROTOCOL & INFORMATION OFFICE
[name].
[name].
[name], M.S.
[name]
[name]
[name]
[name] - CALGB
[name] - ECOG
[name] - Wyeth
[name] - Biologics

**Southwest
Oncology Group**

A National Clinical Research Group

Distribution Date: June 1, 2010
CTEP Submission Date: May 26, 2010

TO: ALL SOUTHWEST ONCOLOGY GROUP MEMBER, CCOP AND
AFFILIATE MEDICAL ONCOLOGISTS AND PATHOLOGISTS; CTSU

FROM: [name], Protocol Coordinator

RE: **S0535**, "A Phase II Study of ATRA, Arsenic Trioxide and Gemtuzumab
Ozogamicin in Patients with Previously Untreated High-Risk Acute
Promyelocytic Leukemia" Study Coordinators: Drs. [name], [name], [name], and [name].

REVISION #6

Study Coordinator: [name].
[contact]
E-mail: [contact]

IRB Review Requirements

- () Full board review required. Reason:
- () Initial activation
 - () Increased risk to patient
 - () Complete study redesign
 - () Addition of tissue banking requirements
 - () Study closure due to new risk information
- () Expedited review allowed
- () No review required

REVISION #6

The above-referenced protocol has been revised as follows:

1. Title Page: The Version Date has been updated.
2. Pages 6-8b, Section 3.2b: The toxicity information for arsenic trioxide has been replaced by the CAEPR Version 2.0 (March 26, 2010).

CTEP has issued an updated CAEPR for arsenic trioxide. This study did not contain a CAEPR previously; therefore, a significant number of risks have been added. However, this information is considered to be similar to the risk information already communicated to patients in the Model Consent Form.

Pages 8a-8b have been added to prevent extensive repagination.

Operations Office

[name] • San Antonio, TX 78229 • [contact] • [contact] • <http://swog.org>

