5.1 Initial Registration

- _____ a. Patients must have a morphologically confirmed diagnosis of high risk (see Section [4.2c](#)) acute promyelocytic leukemia (APL), based on bone marrow examination performed within 14 days before registration. The WBC confirming high risk must be obtained within 14 days prior to registration.
- _____ b. Patients who are known to be PML- RAR α negative by the RT-PCR assay required in Section [5.1g](#) below are not eligible. (NOTE: If the RT-PCR result is indeterminate, additional blood specimens should be submitted for RT-PCR testing to avoid indeterminate pretreatment results whenever possible; if the RT-PCR result remains indeterminate after the initial and any additional specimens are assayed, the patient will be eligible provided all other eligibility criteria are met. Patients may be registered before the RT-PCR assay result is known, but if the result is negative they must be removed from protocol treatment and treated at the physician's discretion; see Section [7.3d](#).)
- _____ c. Patients must have reached their 18th birthday.
- _____ d. Patients must not have prolonged QTc > 0.47 seconds.
- _____ e. Patients must not have received prior systemic chemotherapy for acute leukemia, with the exception of the ATRA, which may be administered for up to 5 days prior to registration. Administration of hydroxyurea, corticosteroids, or leukapheresis to control high cell counts prior to registration is permitted.
- _____ f. Pretreatment cytogenetics must be performed on all patients. Participation in cytogenetic studies is mandatory for patients affiliated with CALGB or ECOG. Collection of pretreatment specimens must be completed within 14 days prior to registration to **S0535**. Note that there are also additional time points at which specimens are required to be submitted for cytogenetics (see Section [15.2](#)). Collection and submission of required materials must be by one of the following mechanisms:
- SWOG Sites and Other Sites not Affiliated with ECOG or CALGB: Specimens must be submitted to each institution's preferred cytogenetics laboratory (see Section [15.2](#)).
 - ECOG Sites: Baseline karyotypes must be submitted via **E3903**. Register patient to **E3903** PRIOR to registration to **S0535**. The ECOG patient number will be required at the time of **S0535** registration (see Section [15.3](#)).

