7.3 Induction Chemotherapy

AGENT	DOSE	ROUTE	Time	NOTES
ATRA ^ζ	45 mg/m ² /day (in 2 doses, 22.5 mg/m ² every 12 hours)	PO	every 12 hrs, Day 1 to CR *	With food. See Section 7.3a below.
Gemtuzumab Ozogamicin ^Δ	9 mg/m ²	IV infusion over 2 hours	Day 1 only ^π	
Arsenic Trioxide	0.15 mg/kg/d	IV infusion over 2 hours	5 days/wk beginning on Day 10 and continuing until CR ^ψ	

* For maximum of 90 days, unless prohibited by either unacceptable toxicity or progressive disease.

^π G.O. may be delayed until Day 6 pending confirmation of APL diagnosis by FISH/cytogenetics, or RT-PCR. Hydroxyurea may be utilized during this time, up to 24 hours prior to initiation of gemtuzumab ozogamicin.

^ψ For a maximum of 60 days, unless prohibited by either unacceptable toxicity or progressive disease.

^Δ Recommended premedications prior to gemtuzumab: acetaminophen 1 gm orally, diphenhydramine 50 mg IV, and methylprednisolone 125 mg IV.

^ζ Day 1 of treatment will be the first day the patient is treated with ATRA, regardless of patient's registration status.

a. ATRA will be "rounded" up to the nearest 10 mg, divided into 2 daily doses, given orally every 12 hours with food.

b. **ATRA syndrome:** A spectrum of clinical manifestations of a cardiorespiratory distress syndrome has been described, including respiratory distress, hypoxemia, fever, erythematous rash, pulmonary infiltrates, pleural or pericardial effusions, congestive heart failure with impaired myocardial contractility and episodic hypotension. Patients with this syndrome may develop rapidly progressive cardiopulmonary failure.

If this syndrome is suspected, ATRA should be held and dexamethasone 10 mg IV or PO BID will be given for 3 days. ATRA will be resumed once the signs/symptoms of the syndrome have resolved. Patients with persistent signs/symptoms of the ATRA syndrome after 3 days of dexamethasone or who have recurrence of the ATRA syndrome after restarting ATRA should be discussed with the Study Chair.

- c. **Prolonged QT_c:** Prolongation of the QT_c has been reported with the use of arsenic trioxide in association with electrolyte abnormalities. Therefore, any identified electrolyte abnormalities of potassium, calcium, or magnesium should be promptly corrected to within normal limits prior to and during treatment with arsenic trioxide. EKG must be obtained twice weekly during induction therapy and as clinically indicated.

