7.8 Assessment of Response

a. Induction

A bone marrow aspirate and biopsy will be obtained at the time of neutrophil recovery ($\geq 1,000/\text{mcl}$) or on Day 42 after beginning protocol ATRA (i.e. not counting any days of ATRA given prior to the patients registration to this study), whichever comes first. Specimens of marrow aspirate (or peripheral blood if dry tap) must be submitted for cytogenetics (for patients affiliated with CALGB or ECOG) and PCR (for all patients) as described in Section [15.0](#). Subsequently, the bone marrow aspirate and biopsy will be repeated every 2 weeks until criteria for CR are met. These subsequent samples will NOT be submitted centrally for cytogenetic or RT-PCR testing, but the tests will still be performed locally. Testing for clinical/hematological CR should be performed locally for all of these subsequent specimens. Patients will continue ATRA and arsenic trioxide until CR is achieved, up to a maximum of 90 days. Patients with a CR will proceed to consolidation therapy as outlined above in Section [7.4](#).

b. Consolidation

A bone marrow aspirate and biopsy will be obtained within 8 weeks (preferably within 4 weeks) preceding Consolidation Cycle 1. This should be performed at the time when peripheral blood counts have recovered to baseline or as clinically indicated. A bone marrow aspirate and biopsy are also required prior to Consolidation Cycle 3. The pre-Consolidation Cycle 3 specimens of marrow aspirate (or peripheral blood if dry tap) must be submitted for PCR as described in Section [15.0](#).

c. Maintenance

A bone marrow aspirate and biopsy will be obtained within 8 weeks (preferably within 4 weeks) prior to beginning maintenance therapy. Specimens of marrow aspirate (or peripheral blood if dry tap) must be submitted for PCR testing as described in Section [15.0](#).

- d. A bone marrow aspirate and biopsy will be obtained every 3 months during Maintenance therapy. Specimens from these samples should NOT be submitted for RT-PCR testing or cytogenetics. Testing for clinical/hematological CR for these samples should be performed locally.

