10.7 Event-free survival (EFS) at 3 years

For this study, EFS at 3 years is defined as a binary variable as follows: Yes if the patient achieves CR (Section [10.2](#)) and remains in continuous CR until at least 3 years after entering the study; otherwise No.

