11.0 STATISTICAL CONSIDERATIONS

11.1 Primary Objective

The primary objective of this study is to test whether the regimen incorporating ATRA, arsenic trioxide, and gemtuzumab ozogamicin is sufficiently safe and effective among patients with previously untreated high-risk acute promyelocytic leukemia to warrant Phase III study. This objective will be met by analyzing the probabilities of continuous complete remission (CCR) at 3 years and of death from any cause within the first 6 weeks of protocol treatment. If the 3-year CCR rate is sufficiently high AND the 6-week mortality rate is sufficiently low, then Phase III study might be warranted; otherwise further study would not be recommended. To define a test criterion based on both outcomes, it is necessary to define null and alternative hypotheses in terms of the joint distribution of efficacy and toxicity.

The regimen would not warrant Phase III study if its true 3-year CCR rate is 50% or less OR its 6-week mortality rate is 30% or more. Therefore, the joint distribution of the null hypothesis with marginal probabilities is the following:

CLOSED EFFECTIVE 06/01/2013

Null Hypothesis Joint Distribution:

Death within first 6 weeks	Died or relapsed within 3 years, or no CR	Alive in CR at 3 years
Yes	30%	0%
No	20%	50%

The regimen would warrant Phase III study if its true 3-year CCR rate is 70% or higher AND its true fatal toxicity rate is 15% or less. Therefore, the joint distribution of the alternative hypothesis with marginal probabilities is the following:

Alternative Hypothesis Joint Distribution:

Death within first 6 weeks	Died or relapsed within 3 years, or no CR	Alive in CR at 3 years
Yes	15%	0%
No	15%	70%

Because there is only limited Group-wide experience with this regimen, accrual will be conducted in two steps. In the first step, 32 eligible patients will be accrued. If more than seven of these patients die within the first 6 weeks, then the study will be terminated early with the conclusion that the study does not warrant Phase III study. Otherwise an additional 38 eligible patients will be accrued. Patients enrolled before RT-PCR results are known and who are subsequently found to be negative for PML-RAR α and RAR α -PML will not be counted towards these accrual goals.

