 - b. Institutions must be identified as approved for registration.
 - c. Registrations may not be cancelled.
 - d. Late registrations (after initiation of treatment) will not be accepted.

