Effective with Revision #5, submission of specimens for cytogenetic studies through protocol **SWOG-9007** is no longer required. Cytogenetic studies must still be performed at each institution's preferred cytogenetics laboratory, according to the schedule in Section 15.1, and reports of the results must be submitted as described in Section [14.0](#).

b. PCR testing

1. Effective with Revision #5, submission of specimens for RT-PCR testing through protocol **S9910** is no longer required. However, RT-PCR testing must still be performed at the following times:

- a. Pretreatment (prior to Induction)
 - b. At the time of neutrophil recovery ($\geq 1,000/\text{mcl}$) or on Day 42 after beginning ATRA (whichever comes first). (See Section 7.8a.)
 - c. Prior to Consolidation #3 (within 8 weeks [preferably within 4 weeks] before starting Consolidation #3 treatment; see Section 7.8b)
 - d. Prior to Maintenance
 - e. At Relapse
2. Specimens for PCR testing may be submitted to any CLIA-approved laboratory; reports of the results must be submitted as described in Section 14.0. CLIA certificates will be verified at the time of an audit.

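### Does the footnote that puts Day 1 at first ATRA leave the start of the 6-week mortality window open?

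*Combined protocol and SAP*

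**What the plan says.** - **11.1** bases the decision on 3-year continuous complete remission (CCR) and on "death from any cause within the first 6 weeks of protocol treatment". Accrual stops if 8 or more of the first 32 patients die in that window. At the end, Phase III is warranted if at least 41 of 70 are in CCR and at most 16 died early.
- **7.3**, footnote to ATRA in the induction table: "Day 1 of treatment will be the first day the patient is treated with ATRA", regardless of registration status.
- **5.1e** bars earlier systemic chemotherapy "with the exception of the ATRA, which may be administered for up to 5 days prior to registration".
- **7.8a** times the Day 42 marrow from protocol ATRA, "not counting any days of ATRA given prior to the patients registration to this study".
- **10.7** defines the other primary outcome by whether the patient "remains in continuous CR until at least 3 years after entering the study". **10.10** times death from the date of registration.
- **13.1** requires registration before Induction and at most one working day before the planned start. **13.4d** adds: "Late registrations (after initiation of treatment) will not be accepted".
- **15.2b and 15.4a** time a PCR specimen at neutrophil recovery "or on Day 42 after beginning ATRA (whichever comes first"), and both then refer the reader to 7.8a.

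**The concern.** The protocol defines one primary outcome in Section 10 and leaves the other without a time origin. The only sentence that says outright what Day 1 of treatment is puts it at first ATRA, which may fall up to 5 days before registration.

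The choice of clock is not neutral. A registered patient has necessarily survived the days before registration. On a first-ATRA clock, up to 5 of the 42 days can therefore contribute no counted death, and deaths on about days 38 to 42 after registration drop out of the early-death count. They remain CCR failures, so only the mortality rule is affected. If the 30% and 15% rates in 11.1 refer to a post-registration window, the shift can only favour the regimen, and the final rule turns on a single count (16 against 17).

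**Working it through.** **1. Which start date does the text support?**

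| Place | What it times | Start it implies |
|---|---|---|
| 11.1 | early death | start of protocol treatment |
| 10.10 | time to death | registration |
| 10.7 | 3-year CCR | study entry |
| 7.8a | Day 42 marrow | protocol ATRA, after registration |
| 13.1, 13.4d | order of registration and treatment | treatment follows registration |
| 15.2b, 15.4a | PCR specimen | by reference to 7.8a |
| 7.3 footnote | dosing days in the induction table | first ATRA |

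Sections 5.1e and 13.4d can both hold only if ATRA given before registration is not protocol treatment, which is how 7.8a uses the word protocol. The footnote's purpose is visible in the Revision #11 memorandum. The same revision extended the ATRA allowance from 3 to 5 days, added the Day 1 footnote, and moved the latest gemtuzumab day from Day 5 to Day 6. The footnote keeps the dosing calendar coherent.

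The two post-registration readings, from registration or from first protocol dose, differ by at most about one working day (13.1).

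**2. Reproduce the design.** Each patient is an early death (probability p), in CCR at 3 years (q), or neither (1 − p − q).

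- P(stop) = P(Bin(32, p) ≥ 8).
- P(pass) = Σ over d₁ ≤ 7 and c₁ of P(D₁ = d₁, C₁ = c₁) × P(D₂ ≤ 16 − d₁, C₂ ≥ 41 − c₁), with trinomial counts of sizes 32 and 38.
- Null (p = 0.30, q = 0.50): stop 0.788, pass 0.0326.
- Alternative (p = 0.15, q = 0.70): stop 0.096, pass 0.887.

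These match the 0.79, 0.033, 0.096 and 0.89 in 11.1.

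**3. Apply the first-ATRA clock to the second stage.** The Revision #7 memorandum reports that "this study has met the criteria to proceed to the second stage of accrual". The footnote came later, with Revision #11, so the stage 1 decision was not taken under it. Suppose a share s of second-stage early deaths falls outside the window. Then p₂ = p(1 − s) and q is unchanged. The documents give no timing of deaths, so s is assumed:

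- 2%: deaths concentrated early;
- 3/42 = 7.1%: deaths spread evenly, every patient with 3 days of earlier ATRA;
- 5/42 = 11.9%: the same with 5 days.

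| s | p₂ under null | False-positive probability | Given stage 1 passed (÷ 0.2118) | Power |
|---|---|---|---|---|
| 0 | 0.300 | 0.0326 | 0.154 | 0.887 |
| 2% | 0.294 | 0.0338 | 0.160 | 0.888 |
| 7.1% | 0.279 | 0.0368 | 0.174 | 0.890 |
| 11.9% | 0.264 | 0.0393 | 0.185 | 0.892 |

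If only half the second-stage patients had earlier ATRA, the false-positive probability is 0.033 (s = 2%) to 0.036 (s = 11.9%).

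**4. Bound.** With stage 1 left as decided and the final death rule removed altogether, the false-positive probability is 0.047. No recount of early deaths at the final analysis, in either stage, can exceed that.

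**5. Opposite mismatch.** If the 30% and 15% rates had been set on a first-ATRA clock and second-stage deaths were counted from registration, then p₂ = p/(1 − s). The false-positive probability falls to between 0.031 and 0.023, and power to between 0.886 and 0.875.

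**The case for a change.** The strongest case for a change is that no sentence states the start date, the one explicit Day 1 definition gives the wrong one, and a single added line would settle it using dates already collected. With a cut-off at 16 deaths, a death around day 40 after registration could be counted or not at the analyst's choice. If the shift is applied to both stages, with a constant hazard and all patients given 5 days of earlier ATRA, the null early-death rate becomes 1 − 0.70^(37/42) = 27.0%. The false-positive probability is then 0.052, and early stopping under the null falls from 0.79 to 0.66.

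The absence of an explicit start date stands. The rest carries less weight. The 0.052 re-runs stage 1 under a footnote that did not exist when stage 1 was decided. The 11.9% loss needs every second-stage patient at a 5-day limit that arrived only with Revision #11. Accrual had reopened on January 4, 2011 under the 3-day limit, and the memoranda, which run newest first, place Revision #11 above one dated November 1, 2011. The Day 42 wording in 15.2b and 15.4a is no further conflict, because both cite 7.8a, which supplies the exclusion. An analyst who follows 11.1 and Section 10 would need to import a dosing footnote into an endpoint to reach the earlier start.

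**Conclusion.** No change is needed. Section 11.1 ties the window to protocol treatment, and the endpoint and registration sections place that at or just after registration. Only the 7.3 footnote differs, and it serves the induction dosing calendar. No figure in 11.1 is wrong: the error rates and power reproduce.

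The contrary reading would raise the false-positive probability from 0.033 to at most 0.039 and power from 0.887 to 0.892. This rests on three assumptions: stage 1 stands as decided, early deaths are spread evenly over 42 days, and all 38 second-stage patients had 5 days of earlier ATRA. If early deaths cluster in the first weeks or fewer patients were pre-treated, the effect is smaller. A line in Section 10 naming the start date would be tidy, but it would only write down what the protocol already implies.

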7.7 Maintenance Therapy

- a. Patients who remain in A1 bone marrow, B1 peripheral blood, and C1 extramedullary disease status (see Section [10.1](#)), may be eligible for registration to maintenance therapy (see Section [5.3](#)). Maintenance should be started no earlier than 2 weeks and no later than 8 weeks after recovery of ANC > 1,000/mcl (1.0 x 10⁹/L) and platelets > 100,000/mcl (100 x 10⁹/L).

b. Maintenance Treatment Plan

AGENT	DOSE	ROUTE	Time	NOTES
ATRA	45 mg/m ² /day (in 2 doses, 22.5 mg/m ² every 12 hours)	PO	Days 1-7 every 14 days	With food. See Section 7.7c below.
6-MP	60 mg/m ² /d	PO	Daily	For 1 year
Methotrexate	20 mg/m ²	PO		Once per week for 1 year.

- c. ATRA will be “rounded” up to the nearest 10 mg, divided into 2 daily doses, given orally every 12 hours with food.
- d. Prior ATRA syndrome: Patients who experienced the ATRA syndrome during induction may receive ATRA during Maintenance, since the ATRA syndrome is not expected to occur during remission.

7.8 Assessment of Response

a. Induction

A bone marrow aspirate and biopsy will be obtained at the time of neutrophil recovery ($\geq 1,000/\text{mcl}$) or on Day 42 after beginning protocol ATRA (i.e. not counting any days of ATRA given prior to the patients registration to this study), whichever comes first. Specimens of marrow aspirate (or peripheral blood if dry tap) must be submitted for cytogenetics (for patients affiliated with CALGB or ECOG) and PCR (for all patients) as described in Section [15.0](#). Subsequently, the bone marrow aspirate and biopsy will be repeated every 2 weeks until criteria for CR are met. These subsequent samples will NOT be submitted centrally for cytogenetic or RT-PCR testing, but the tests will still be performed locally. Testing for clinical/hematological CR should be performed locally for all of these subsequent specimens. Patients will continue ATRA and arsenic trioxide until CR is achieved, up to a maximum of 90 days. Patients with a CR will proceed to consolidation therapy as outlined above in Section [7.4](#).

b. Consolidation

A bone marrow aspirate and biopsy will be obtained within 8 weeks (preferably within 4 weeks) preceding Consolidation Cycle 1. This should be performed at the time when peripheral blood counts have recovered to baseline or as clinically indicated. A bone marrow aspirate and biopsy are also required prior to Consolidation Cycle 3. The pre-Consolidation Cycle 3 specimens of marrow aspirate (or peripheral blood if dry tap) must be submitted for PCR as described in Section [15.0](#).

c. Maintenance

A bone marrow aspirate and biopsy will be obtained within 8 weeks (preferably within 4 weeks) prior to beginning maintenance therapy. Specimens of marrow aspirate (or peripheral blood if dry tap) must be submitted for PCR testing as described in Section [15.0](#).

- d. A bone marrow aspirate and biopsy will be obtained every 3 months during Maintenance therapy. Specimens from these samples should NOT be submitted for RT-PCR testing or cytogenetics. Testing for clinical/hematological CR for these samples should be performed locally.

- e. A bone marrow aspirate will be obtained every 3 months for the first year following completion of maintenance therapy, every 6 months for the second year following completion of maintenance therapy and at the end of the third year following completion of maintenance therapy. At the time of relapse cytogenetic studies and RT-PCR testing must be performed as described in Section [15.0](#).

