October 1, 2015

GROUP CHAIR'S OFFICE

[name]
CHAIR

[name]
MC: L586
Portland, OR 97239

[contact]
[contact] FAX

OPERATIONS OFFICE

[name]
Suite 250
San Antonio, TX 78229

[contact]
[contact] FAX

STATISTICAL CENTER

[name]
Suite 1900
Seattle, WA 98101

[contact]
[contact] FAX

[name]
M3-C102
[name]
Seattle, WA 98109

[contact]
[contact] FAX

swog.org

TO: ALL NATIONAL CLINICAL TRIALS NETWORK (NCTN) MEMBERS
FROM: [name], MIIM, Protocol Coordinator (E-mail: [contact])
RE: **S0535**, "A Phase II Study of ATRA, Arsenic Trioxide and Gemtuzumab Ozogamicin in Patients with Previously Untreated High-Risk Acute Promyelocytic Leukemia" Study Chairs: Drs. [name], [name], [name], [name], and [name].

MEMORANDUM

Study Chair: [name].
[contact]
E-mail: [contact]

IRB Review Requirements

- Full board review required. Reason:
 - Initial activation (should your institution choose to participate)
 - Increased risk to patient
 - Complete study redesign
 - Addition of tissue banking requirements
 - Study closure due to new risk information
- Expedited review allowed
- No review required

MEMORANDUM

The purpose of this memorandum is to clarify the intended timing of patient follow-up for **S0535**. All patients must be followed until death or a maximum of 3 years from time of initial patient registration (as indicated in Section 7.13 of the protocol).

There is a discrepancy in the follow-up language between the protocol (Section 7.13), which is correct, footnote (Θ) in Section 9.0, and the Model Consent Form language on Page 6, under "How long will I be in the study?." This discrepancy occurred due to a protocol change prior to the initial activation of the protocol. At that time, the update was inadvertently omitted from the footnote in Section 9.0 and the Model Consent Form (MCF).

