7.13 Follow-Up Period

All patients will be followed until death or a maximum of 3 years from time of initial registration.

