9.0 STUDY CALENDARS

REQUIRED STUDIES	PRE-STUDY	INDUCTION	CONSOLIDATION #1 through 2		CONSOLIDATION #3 through 4		CONSOLIDATION #5 through 6		MAINTENANCE		Follow Up
			Prior	During	Prior	During	Prior	During	Prior	During	
PHYSICAL											
History & Physical Exam	X	2X/week	X	X&	X	X α	X	X&	X	X&	X√
Height, Weight and BSA	X		X	X†	X	X†	X	X†	X	X&	X√
Performance Status (Zubrod)			X	X&	X	X α	X	X&	X	X&	X√
Toxicity Notation		2X/week	X		X		X		X	X&	X√
LABORATORY STUDIES											
CBC, Diff, Plts	X	2X/week	X	weekly	X	weekly	X	weekly	X	X&	X√
Pregnancy test	X										
Electrolytes (incl. Ca ⁺ and Mg ⁺⁺), creatinine *	X	2X/week	X	weekly	X	weekly	X	weekly	X	X&	
Bilirubin, AST, ALT, Alkaline phosphatase *	X	2X/week	X	weekly	X	weekly	X	weekly	X	X&	
Cholesterol, triglycerides *	X				X		X		X	X&	
PTT, PT, fibrinogen, FDP, D-dimer Δ *	X	2X/week									
BM Aspirate/Biopsy ⊖	X	X ψ	X		X				X	XΠ	X
Cytogenetics Σ	X	X ú									X¿
RT-PCR for PML-RARα Σ	X	X			X†				X		X¿
Lumbar Puncture (see Section 7.2b)			X								
X-RAYS AND SCANS											
Chest X-Ray %	X										
MUGA/ECHO					X#						
EKG \$	X	2X/week			X						
TREATMENT (See Section 7.0)											
Allopurinol/rasburicase		X									
ATRA		X f				X				X	
Daunomycin						X					
Arsenic trioxide		X		X							
6-mercaptopurine										X	
Methotrexate										X	
Gemtuzumab ozogamicin		X						X			

NOTE: Forms are found in Section 18.0. Forms submission guidelines are found in Section 14.0.

Click here to view [footnotes](#).

Footnotes:

- * Results of these tests do not determine eligibility but should be done prior to registration in accordance with good medical practice.
- & Monthly.
- √ After the patient is off treatment, the remaining of Months 3, 6, 9, 12, 18, 24 and 36 from the time of initial registration.
- Δ These tests should be done at pretreatment, twice weekly during induction until normal, and as clinically indicated thereafter.

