- ⊖ Pretreatment, during induction (on Day 42, then q 2 wks until CR is met), prior to Consolidation #1, prior to Consolidation #3, prior to Maintenance, then every 3 months during maintenance. Once maintenance is complete, every 3 months for the 1st year, then every 6 months for the 2nd year, then at the end of the 3rd year from registration. Following completion of maintenance, only aspirate is required. Note that the marrow documenting CR may serve as the prior to Consolidation #1 marrow, providing it was performed within 8 weeks prior to Consolidation registration (see Section [5.2](#)).
- Σ See Section [15.0](#).
- % Chest X-Ray should be done pretreatment and as clinically indicated.
- \$ Obtain within 72 hours prior to the day of treatment. To be performed twice per week for the first 2 weeks of induction, prior to consolidation Cycle 3, and thereafter as clinically indicated.
- ψ On Day 42, then every 2 weeks until criteria for CR are met.
- π Every 3 months during maintenance.
- α Every 2 weeks.
- # See Section [7.5c](#).
- † To be performed prior to each cycle of consolidation.
- f ATRA administration is permitted for up to 5 days prior to registration.
- ¶ RT-PCR required prior to Consolidation #3, but not #4.
- ¿ Follow-up cytogenetics and RT-PCR required at relapse only.
- ü Only submitted centrally for patients affiliated with CALGB or ECOG (see Section [7.8a](#)).

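### Section 7.8e still counts post-maintenance marrows from the end of maintenance, while follow-up and the 3-year endpoint run from registration, and the sponsor's correction leaves it out

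*Combined protocol and SAP*

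**What the plan says.** Section 7.8e sets the marrow schedule after treatment: "A bone marrow aspirate will be obtained every 3 months for the first year following completion of maintenance therapy", then "every 6 months for the second year following completion of maintenance therapy", then a last one "at the end of the third year following completion of maintenance therapy". All three parts count from the end of maintenance.

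The other relevant sections end at 3 years from registration:

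- Section 7.13: "All patients will be followed until death or a maximum of 3 years from time of initial registration".
- Section 10.7: a patient is a success on the primary endpoint if he or she reaches CR and "remains in continuous CR until at least 3 years after entering the study".
- Section 9.0, marrow footnote Θ: after the quarterly and half-yearly marrows, "then at the end of the 3rd year from registration".
- Section 9.0, visit footnote: after treatment, "the remaining of Months 3, 6, 9, 12, 18, 24 and 36 from the time of initial registration". Section 14.4m asks for the Follow Up Form at the same months.

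The memorandum of October 1, 2015 at the front of the document says: "There is a discrepancy in the follow-up language between the protocol (Section 7.13), which is correct". It goes on to name footnote Θ and the Model Consent Form as the places where an update had been missed. In footnote Θ it replaces maintenance by treatment as the event that starts the schedule. It does not mention 7.8e.

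**The concern.** The primary efficacy count is the number of patients still in continuous CR 3 years after entry, and Section 11.1 compares it with a fixed cutoff of 41 of 70. Under Section 10.6 a relapse with no circulating blasts and no extramedullary disease has to be found in the marrow or by molecular testing, so the timing of marrows near Month 36 bears on who is counted.

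A site that reads the treatment section finds a marrow schedule that is not tied to Month 36 and runs on well past the follow-up limit. A site that reads the calendar finds a marrow at the end of the third year from registration. The marrows that 7.8e places after Month 36 are invasive, and no planned analysis uses them. Section 7.8e also starts only when maintenance is completed. It therefore gives no schedule for a patient who stops earlier, for example for toxicity under Section 7.11d, although 7.13 still follows that patient.

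**Working it through.** **The plan's own figures.** The documents give no figure for the marrow schedule. The design figures in Section 11.1 do use 3-year status, so they were checked first. With early-death probability p and 3-year CCR probability c:

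- Early stopping = P(Bin(32, p) ≥ 8).
- Success = sum over d1 ≤ 7 and d1 + d2 ≤ 16 of P(Bin(32, p) = d1) × P(Bin(38, p) = d2) × P(Bin(70 − d1 − d2, c/(1 − p)) ≥ 41).
- Null (p = 0.30, c = 0.50): 0.788 and 0.0326, against 0.79 and 0.033 in the plan.
- Alternative (p = 0.15, c = 0.70): 0.0958 and 0.887, against 0.096 and 0.89.

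These agree. Marrow timing does not enter them.

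**When maintenance ends.** Let M be the month from registration at which maintenance ends. The protocol gives these inputs:

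- Induction of at most 90 days (7.8a).
- CR to Cycle 1 of at most 8 weeks (7.4a).
- Cycles 1 and 2 of 5 + 2 + 5 = 12 weeks (7.4b).
- Cycle 2 to Cycle 3 within 4 weeks if possible (7.5a).
- A gap of 2 to 8 weeks after count recovery before Cycles 4, 5 and 6 and before maintenance (7.5b, 7.6a, 7.6b, 7.7a).
- Maintenance of 1 year (7.7b).

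Time to CR and count-recovery times are assumptions: induction 4 to 12.9 weeks, recovery 2 to 5 weeks after Cycles 3 and 4, and 2 to 8 weeks after Cycles 5 and 6. All six cycles are assumed given. M = weeks × 7 / 30.4375.

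| Course | Induction | To Cycle 1 | Cycles 1–2 | To Cycle 3 | Cycles 3–4 (recovery + gap) | Cycles 5–6 (recovery + gap) | Maintenance | Weeks | M |
|---|---|---|---|---|---|---|---|---|---|
| Fastest | 4 | 0 | 12 | 0 | 2 × (2 + 2) | 2 × (2 + 2) | 52 | 84 | 19.3 |
| Fast | 5 | 1 | 12 | 2 | 2 × (3 + 2) | 2 × (4 + 2) | 52 | 94 | 21.6 |
| Middle | 6 | 4 | 12 | 4 | 2 × (4 + 3) | 2 × (6 + 3) | 52 | 110 | 25.3 |
| Slow | 12.9 | 8 | 12 | 4 | 2 × (5 + 8) | 2 × (8 + 8) | 52 | 146.9 | 33.8 |

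**Where the 7.8e marrows fall.** They are due at M + 3, 6, 9, 12, 18, 24 and 36. The last one passes the Month 36 limit by (M + 36) − 36 = M months.

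| M | 7.8e marrows (month from registration) | Last one before Month 36 | After Month 36 |
|---|---|---|---|
| 19.3 | 22.3, 25.3, 28.3, 31.3, 37.3, 43.3, 55.3 | 31.3 (4.7 months earlier) | 3 of 7 |
| 21.6 | 24.6, 27.6, 30.6, 33.6, 39.6, 45.6, 57.6 | 33.6 (2.4 months earlier) | 3 of 7 |
| 25.3 | 28.3, 31.3, 34.3, 37.3, 43.3, 49.3, 61.3 | 34.3 (1.7 months earlier) | 4 of 7 |
| 33.8 | 36.8, 39.8, 42.8, 45.8, 51.8, 57.8, 69.8 | none | 7 of 7 |

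In the slow course the nearest earlier marrow is one of the three-monthly marrows during maintenance (7.8d). If one is taken as maintenance ends, it falls 36 − 33.8 = 2.2 months before Month 36.

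Within this range a 7.8e marrow lands exactly on Month 36 only when M is 36 − 12 = 24, 36 − 9 = 27, 36 − 6 = 30 or 36 − 3 = 33. For M from 18 to 24 the last one before the endpoint is at M + 12, so the gap is 24 − M months: 3 months at M = 21, approaching 6 as M nears 18.

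**The corrected footnote.** It starts at the end of treatment and ties the last marrow to registration. It does not say from which date its first and second years are counted. If they too were counted from the end of treatment, then at M = 25.3 the marrows at 37.3, 43.3 and 49.3 would again fall after Month 36.

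**The case against.** The best defence is that 7.13 sets a maximum and the sponsor has said in writing that 7.13 is the correct text. A site that reads both sections would stop at Month 36, so the later marrows in 7.8e are leftover wording. For patients who complete maintenance, the printed footnote Θ also begins at the end of maintenance with the same first intervals, so the two schedules differ mainly in how they end. Relapse is not sought by marrow alone: Section 10.6 also counts blood blasts and extramedullary disease, and the calendar has an examination and blood count at Month 36. All of this stands, and it is why the effect on the endpoint is small. It does not remove the conflict, because 7.8e is current text and the memorandum that set out to resolve the discrepancy does not name it.

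A reader might infer three stronger things that the documents do not support:

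- **That the protocol has no marrow at Month 36.** Footnote Θ places one at the end of the third year from registration, and a 7.8e marrow falls there by chance when, for example, M = 24.
- **That sites split between the two schedules and the 3-year count is materially biased, or that patients had useless marrows.** No passage shows what sites did. The memorandum says only that sites will not be cited for differences in follow-up period arising from the discrepancy.
- **That the sponsor meant to drop timing from the end of therapy.** The corrected footnote keeps an end-of-treatment start and ties only the last marrow to registration.

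**Conclusion.** Section 7.8e is wrong as written: an internal inconsistency of minor severity. Its last marrow falls M months after follow-up has ended. With M of about 19 to 34 that is roughly 1.6 to 2.8 years, and 3 to 7 of the 7 marrows come after Month 36. The range for M rests on the assumed induction and recovery times and on all six cycles being given. Where cycles are omitted (7.5d, 7.6c, 8.4d) M is shorter, but the overrun still equals M, so it does not disappear.

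For patients who complete maintenance at about Month 21 or later, a marrow under 7.8e or 7.8d usually falls within about 3 months before the endpoint date. The effect on the continuous-CR count is therefore likely modest. For patients who stop before completing maintenance, 7.8e is silent. The alpha, power and sample size figures are unaffected.

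**What to change.** Reconcile 7.8e with 7.13, 10.7 and footnote Θ as the memorandum corrects it. The result should be a single marrow schedule that is consistent with the stated follow-up limit and the 3-year endpoint, covers patients who leave treatment early, and places no protocol marrow after follow-up ends. The text should also state the date from which each year of the schedule is counted, since the corrected footnote leaves that open for the first two years. The choice of schedule belongs to the sponsor.

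The cost is wording in 7.8e and, if needed, footnote Θ. It would take out the marrows now written for after Month 36. It may not be purely a reduction, because a patient managed on 7.8e alone could gain the end-of-third-year marrow that the footnote already requires. Since the study is closed to accrual, the report of the 3-year result should also say which marrow schedule was in force.
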